4.4 Statistical Design and Power

General considerations

All statistical analyses will be estimated using Stata v15 or higher. Descriptive statistics for Aim 1 will be calculated using all available data, and tests of hypotheses for Aim 2 will be performed using intent-to-treat approaches that include all participants randomized to a treatment condition regardless of whether they complete the intervention or not. Following enrollment of the full sample, treatment group differences in baseline demographic and sleep related functioning variables will be tested. Any variables that emerge as being significantly different between the two treatment groups will be included as covariates in all tests of Aim 2. If more than 3 variables emerge as being significantly different between the treatment arms, the full set of demographic and sleep related functioning variables will be used to estimate a propensity score indicating likelihood of membership in We-PAP relative to information control (IC); this propensity score will be included as a covariate in all tests of Aim 2.

Given the pilot nature of the proposed study, significance tests of study hypotheses will be performed using one-sided tests with $\alpha = 0.10$. Research concerning statistical criteria for pilot testing of clinical trials¹¹⁰ suggest that these relaxed statistical criteria, with an emphasis on a priori defined confidence intervals, are appropriate because the primary purposes of the proposed study are to evaluate whether there is reasonable evidence that We-PAP outperforms IC and, if so, to use this initial evidence to plan for a larger scale RCT of We-PAP. We will use these criteria with the primary adherence outcomes as a go/no go threshold for proceeding to a larger scale RCT. Provided that We-PAP outperforms IC as hypothesized, we will continue to use these criteria in estimating the 90% CI of the between group difference to determine the necessary sample size for a subsequent RCT. Because of the well-known phenomenon of pilot trials generating larger effect sizes than follow-on RCTs, we will use the lower limit of the 90% CI to anticipate this reduction in effect size and conservatively plan for a larger study.

Sample Size Determination

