Study sample size was primarily determined by power analyses of primary adherence outcomes (adherence outcomes in patient and patient and partner sleep quality). Adherence outcomes (% nights with CPAP used ≥ 4 hours and numbers of hours of CPAP use per night) are available only for the patient and tests of study hypotheses depend on the precision of estimates of group effects at the highest level of nesting (i.e., the individual). As such, power estimates for tests of treatment effects on these variables were generated for standard linear models rather than MLMs.

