Power estimates were generated using descriptive statistics for behavioral and cognitive behavioral CPAP interventions vs. IC reported in Wozniak et al.¹¹¹. For % nights with CPAP usage ≥ 4 hours, We-PAP adherence was assumed to be 47% and IC adherence was assumed to be 28%. For total hours of CPAP usage per night, We-PAP usage was assumed to be 5.44 hours/night and IC usage was assumed to be 4 hours/night with a SD of 2.12 hours/night within each group. Power estimates based on these assumptions indicate that a sample size of 20 couples per group will provide power of .8 or higher to detect between group differences of $d = .68$ for average hours of CPAP usage and O.R. = 4.36. These required effect sizes are consistent with the medium to large differences in adherence outcomes between behavioral treatments for CPAP and IC reported in Wozniak et al., 2014¹¹¹. Power estimates for patient and partners' sleep [actigraphy and diary-assessed] were generated using descriptive statistics for behavioral and cognitive behavioral CPAP interventions vs. IC as reported in Wozniak et al.,¹¹¹ as well as in Buysse et al.,⁵⁸ and Sweetman et al¹¹². Assumptions for secondary outcomes were: sleep efficiency, We-PAP: $M = 82.2$, $SD = 1.16$, IC: $M = 79.99$, $SD = 1.15$; daytime sleepiness, We-PAP: $M = 4.9$, $SD = 0.3$, IC: $M = 5.2$, $SD = 0.45$. Power estimates for secondary outcomes were not available for differential treatment effects of CBT vs. IC for health-related quality of life, cognitive functioning, or relationship quality. Therefore, consistent with other psychosocial outcomes (e.g., depression, anxiety, etc.), differential treatment effects were assumed to be moderate to large, $d = .7$. The availability of these outcomes for both patients and partners permitted estimation of power for MLMs with adjustment made for assumed associations ($r = .3$) between relationship partners within a couple. Power estimates based on these assumptions indicate that a sample size of 20 couples per group will provide power of .8 or higher to detect between group differences of $d = .54$ for all outcomes, which is smaller than or equal to effect sizes for all outcomes described above.

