A final consideration in the determination of the sample size for the proposed study was the necessary sample size for stable and precise estimates of treatment effects using multilevel modeling. Maas and Hox's (2005)¹¹³ canonical work on necessary sample sizes for group level effects in MLM determines that group sizes of 20 members and larger is sufficient for generating unbiased estimates. Given that primary questions center on treatment effects in the proposed study, 20 couples per treatment ensures an adequate sample size for generating unbiased estimates of treatment effects thus permitting use of MLM to test study hypotheses.

Analysis Plan

Aim 2

Both primary outcomes will be analyzed using a two-level MLMs as described by the following series of equations:

$$\text{Level-1: } Y(\text{Adherence})_{ij} = \beta_{0j} + e_{ij}$$

$$\text{Level-2: } \beta_{0j} = \pi_{0j} + \pi_{0[1 \text{ to } n]} * [\text{covariates determined by tests of between group differences at baseline in demographic and sleep variables}] + \pi_{0[n+1]} * [\text{Treatment}] + \mu_{0j}$$

where i represents daily measures total hours of CPAP use/whether total hours of CPAP ≥ 4 hours (0 = no, 1 = yes) over the 3 month follow-up and j represents individuals. Treatment is a dummy coded variable with 0 = IC and 1 = We-PAP. The level two intercept in this model, π_{0j} , represents the maximum likelihood estimate of average adherence and $\pi_{0[n+1]}$ provides a test of the primary study hypotheses. Separate models will be run for total hours of sleep and ≥ 4 hours of CPAP use as outcomes estimated using models with Gaussian and binomial distributions respectively.

Secondary outcomes will be analyzed using a three-level MLMs as described by the following series of equations:

$$\text{Level-1: } Y(\text{Outcome})_{ijk} = \beta_{0jk} + \beta_{1jk} * (\text{Pre vs. 3 month follow-up}) + e_{ijk}$$

$$\text{Level-2: } \beta_{0jk} = \pi_{00k} + \pi_{0[1 \text{ to } n]k} * [\text{covariates determined by tests of between group differences at baseline in demographic and sleep variables}] + \pi_{0[n+1]k} * (\text{Patient vs. partner}) + \mu_{0jk}$$

$$\beta_{1jk} = \pi_{1jk} + \pi_{1[n+1]k} * (\text{Patient vs. partner})$$

$$\text{Level-3: } \pi_{0jk} = \gamma_{000} + \gamma_{001} * [\text{Treatment}] + r_{00k}$$

$$\pi_{1jk} = \gamma_{100} + \gamma_{101} * [\text{Treatment}]$$

$$\pi_{1[n+1]k} = \gamma_{1[n+1]0} + \gamma_{1[n+1]1} * [\text{Treatment}]$$

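### The SAP bases .8 power at an odds ratio of 4.36 on 47% vs 28% of nights adherent, but those rates give an odds ratio of 2.28, and no power is stated for them

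*SAP*

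**What the plan says.** All of the text concerned is in SAP section 4.4.

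- **Assumed effect.** Under Sample Size Determination, for the percentage of nights with at least 4 hours of CPAP: "We-PAP adherence was assumed to be 47% and IC adherence was assumed to be 28" (per cent). For hours per night the assumption is 5.44 vs 4, with an SD of 2.12.
- **Power claim.** "Power estimates based on these assumptions indicate that a sample size of 20 couples per group will provide power of .8 or higher" to detect d = .68 for hours and, for the 4-hour outcome, "O.R. = 4.36. These required effect sizes are consistent with the medium to large differences in adherence outcomes" that the cited source reports.
- **Basis of the calculation.** For the adherence outcomes, "power estimates for tests of treatment effects on these variables were generated for standard linear models rather than MLMs".
- **Secondary outcomes.** The detectable effect is d = .54, "which is smaller than or equal to effect sizes for all outcomes described above".
- **Planned analysis.** Under Analysis Plan, Aim 2, both primary outcomes go into two-level models of nightly data, "where i represents daily measures total hours of CPAP use/whether total hours of CPAP ≥ 4 hours (0 = no, 1 = yes"), and the two models are "estimated using models with Gaussian and binomial distributions respectively".
- **Use of the result.** Under General considerations, tests are one-sided at 0.10, and "We will use these criteria with the primary adherence outcomes as a go/no go threshold for proceeding to a larger scale RCT".

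**The concern.** The odds ratio attached to the power claim is not the odds ratio of the rates on which the claim is said to rest. For hours, the detectable and assumed effects coincide. For the secondary outcomes, the SAP says outright that the detectable effect is no larger than the assumed ones. Only the 4-hour outcome has a detectable effect larger than the assumed one, and the text does not say so. Because 4.36 stands in the same sentence as d = .68, which does equal its assumption, a reader is likely to take .8 as the power if We-PAP performs as assumed.

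This outcome feeds the go/no-go decision. If power at the assumed effect is below .8, an effective intervention has a higher chance of a no-go on this outcome than the SAP suggests.

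**Working it through.** **Inputs** (SAP 4.4): 20 patients per arm; one-sided alpha 0.10, so z = 1.2816; rates 47% and 28%; hours 5.44 vs 4, SD 2.12; stated odds ratio 4.36.

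**1. Hours outcome, as a check of method.** d = (5.44 − 4)/2.12 = 0.679. The noncentrality is 0.679 × √(20/2) = 2.148 on 38 df, and power is 0.80. The plan's figure reproduces, and the detectable effect equals the assumed one.

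**2. Odds ratio of the assumed rates.** (0.47/0.53)/(0.28/0.72) = 0.8868/0.3889 = 2.28.

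**3. What 4.36 means.**
- Up from 28%: odds 0.3889 × 4.36 = 1.696, so the We-PAP rate is 1.696/2.696 = 62.9%.
- Down from 47%: odds 0.8868/4.36 = 0.2034, so the IC rate is 0.2034/1.2034 = 16.9%.

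Neither pair is the assumed one.

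**4. Single-level power, one yes/no value per patient.** Pooled z: power = Φ{[(p1 − p2) − 1.2816·s0]/s1}, with s0 = √[2p̄(1 − p̄)/20] and s1 = √[p1(1 − p1)/20 + p2(1 − p2)/20].
- 62.9% vs 28%: (0.349 − 1.2816 × 0.1575)/0.1475 = 0.998, power 0.84. A Wald test on the log odds ratio gives 0.81, exact enumeration of the z test 0.84, and Fisher's exact test 0.73.
- 47% vs 16.9%: 0.79 (pooled z) or 0.81 (exact z).
- 47% vs 28%: (0.19 − 1.2816 × 0.1531)/0.1501 = −0.041, power 0.48. Wald gives 0.48, exact z 0.51 and Fisher 0.37.

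So the claim at 4.36 reproduces as power for a detectable effect, most naturally from 28%. At the assumed rates, this basis gives about 0.48. That figure is the extreme in which each patient reaches 4 hours on every night or on none. It is not the power of the planned analysis.

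**5. Patient-level percentage of nights, t-test, 19-point difference.** The between-patient SD is not in the documents, so the values below are assumptions. Noncentrality is (19/SD) × √10 on 38 df.

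| Assumed SD (points) | 20 | 22 | 25 | 28 | 30 | 35 | 40 |
|---|---|---|---|---|---|---|---|
| Power | 0.95 | 0.92 | 0.86 | 0.80 | 0.76 | 0.66 | 0.58 |

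Power reaches .8 only if the SD is about 28 points or less. All-or-none patients would have SDs of √(0.28 × 0.72) = 45 points and √(0.47 × 0.53) = 50 points. Their root mean square is 47.5, giving 0.49 and agreeing with step 4.

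**6. Nightly random-intercept binomial model, as planned.** Simulated with marginal rates held at 28% and 47%, and with 90 nights and no covariates as assumptions. There were 3,000 trials per SD, with Monte Carlo error of at most 0.009.

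| Assumed random-intercept SD (logits) | 1.0 | 1.5 | 1.8 | 2.0 | 2.32 | 3.0 |
|---|---|---|---|---|---|---|
| Power | 0.96 | 0.87 | 0.82 | 0.79 | 0.76 | 0.71 |

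With equal rates of 28%, the test rejected in 0.114 of trials at SD 1.5 and 0.108 at SD 2.32, so these powers are slightly flattering. A subject-specific odds ratio of 4.36 corresponds to 28% vs 47% at an SD of 2.32, where power is 0.76. The documents favour no particular SD.

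**The case against.** The best defence is that nothing is miscalculated. The SAP calls d = .68 and 4.36 required effect sizes and states the power to detect them, which is the language of a minimum detectable effect. The stated IC rate of 28% and the stated single-level basis make the likely derivation clear, and it gives .8 or more by the usual large-sample tests. Underpowering is not shown either: the one low figure is not the power of the planned analysis, and the others straddle .8 on SDs that the documents do not supply. This is a pilot with deliberately relaxed criteria, the go/no-go rule uses the test result and not the power figure, and 20 per arm has a separate justification from multilevel estimation.

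Much of this stands. The figure is sound as power for a detectable effect, 28% is the likeliest base rate, and no shortfall in power is proven. What does not stand is the stated link to the assumptions. The required odds ratio is nearly twice the assumed one (4.36/2.28 = 1.91), and nothing in the SAP says so. Calling it consistent with published differences does not close the gap, because the SAP's own rates, which it attributes to the same source, give 2.28. A subject-specific reading could connect 4.36 to the assumed rates, but it conflicts with the stated single-level basis and needs an SD that the SAP does not give.

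**Conclusion.** The concern holds. The power stated for the 4-hour outcome does not follow from the rates it is said to rest on: 47% vs 28% is an odds ratio of 2.28, whereas 4.36 from 28% means about 63%. No power is given for the assumed rates. On the SAP's single-level basis, with one yes/no value per patient, it would be about 0.48, the worst case. In the planned nightly analysis it ran from 0.96 to 0.71 over assumed logit SDs of 1.0 to 3.0, so the documents do not settle whether .8 is met.

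The fault is confined to this one power statement. The hours outcome reproduces at 0.80 and still supports 20 per group. It should be corrected because the outcome is primary and enters the go/no-go decision.

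**What to change.** In Sample Size Determination:

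1. State that 47% vs 28% is an odds ratio of 2.28, and stop presenting .8 power at 4.36 as following from those rates.
2. State the base rate and type of odds ratio behind 4.36. If it is single-level from 28%, label it a minimum detectable effect (about 63% vs 28%) that exceeds the assumed effect. If another base rate was used, give that pair of rates. If it is subject-specific, say so and give the random-intercept SD.
3. Give the power at 47% vs 28% for the planned nightly model, under a stated between-patient SD or over a stated range that includes favourable and unfavourable values. If 0.48 is cited, label it as the one-value-per-patient figure.

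The cost is a few sentences and one recomputed figure or short range. Sample size, outcomes and analysis stay as they are. The only drawback is that the reported power for this outcome may look less favourable.

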
Describe the project objectives and all the procedures that will be conducted for the proposed project (e.g. participant identification, data collection, data analysis, etc.): [HELP?](#)

Visit schedule: Baseline (pre-treatment), 1 month (questionnaires only), 3 months post PAP initiation. Participants will receive the 3 intervention sessions between baseline and 1 month.

Study design

Overall design: The overarching hypothesis of this study is that patients and partners who complete the couples based sleep health intervention (We-PAP) will have greater PAP adherence, improvements in sleep and quality of life compared to patients and partners with standard care plus information (IC). In this phase 2 trial, we will be adapting and testing the intervention modules then will conduct a 2-arm randomized controlled trial of the novel We-PAP intervention in comparison to IC.

Couples will be randomized in a 1:1 ratio using a randomization table created by the study statistician ([name]). Allocation will be concealed through using the online randomizer module in the RedCap data management system.

The study will be conducted over 20 months. The duration of participation for participants will be 3.5 months. Participants will complete a baseline assessment (pre-treatment), then 3 intervention sessions via telehealth. They will complete questionnaires at 1 month, then complete a final 3 months post treatment initiation assessment. This is a single site trial with multiple recruitment locations at the University of Utah Sleep Center and community clinics in the Salt Lake City area.

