medium sensitivity. The rest period will be calculated by blinded research staff using standardized procedures. The training protocol will ensure that scorers are within an acceptable agreement range before scoring study records. A random sample of 10% of records will be checked for quality control and retraining will be assigned if scoring is not within 90% of the values determined by the co-PI. Participants will be provided with verbal and written instructions as well as links to youtube.com videos with demonstrations. Participants will wear the Actiwatches for 7-10 days in order to maximize the possibility of collecting 7 nights. Data will be considered valid if there are at least 5 nights. After the watches are retrieved, research staff will use the Actiware software program to calculate the following variables: total sleep time, sleep onset time, sleep offset time, sleep duration, sleep efficiency, sleep latency, wake after sleep onset, and sleep fragmentation index. The Actiwatch will be administered with a sleep diary to assist in scoring the rest interval. Cognitive measures administered at baseline and 3-month follow-up include the Repeatable Battery for the Assessment of Neuropsychological Status (RBANS). We will also administer the cognitive difficulties scale to assess for selfreported cognitive problems. Other self-report questionnaires administered at baseline, 1-month and 3-months include: Self-efficacy for sleep apnea, functional outcomes of sleep questionnaire, the Couple Satisfaction Index, PAP tactics questionnaire, PROMIS sleep related impairment, Epworth Sleepiness Scale. Feasibility and acceptability measures: We will use a combination of quantitative and qualitative measures. Outcomes include percentage of participants completing intervention sessions, ratings of ease of participation in the telehealth, questions about the number and duration of sessions, perceived benefits of the intervention and enjoyment of the sessions. We will also ask open ended questions about the format, feedback on the content, materials and general feedback and suggestions for improving the interventions.

Measures

Screening: Potential patients and partners will complete screening measures over the phone or via a web link to verify inclusion/exclusion criteria including demographics, a medical history and medication use questionnaire and various measures for inclusion/exclusion criteria (e.g., sleep disturbance).

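### The planning SDs for sleep efficiency and daytime sleepiness are implausibly small for individual people, so the SAP's claim that d = .54 is no larger than every assumed effect is unsupported for these two outcomes

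*SAP*

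**What the plan says.** Under Sample Size Determination, SAP section 4.4 gives planning values for two secondary outcomes, taken from cited studies: "sleep efficiency, We-PAP: $M = 82.2$, $SD = 1.16$, IC: $M = 79.99$, $SD = 1.15" and "daytime sleepiness, We-PAP: $M = 4.9$, $SD = 0.3$, IC: $M = 5.2$, $SD = 0.45". For quality of life, cognition and relationship quality it found no source values and assumes d = .7.

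The power statement covers patients and partners together, with "adjustment made for assumed associations ($r = .3$) between relationship partners within a couple". It reads "20 couples per group will provide power of .8 or higher to detect between group differences of $d = .54$ for all outcomes", and of that .54 it adds "which is smaller than or equal to effect sizes for all outcomes described above". The test level is set under General considerations: "significance tests of study hypotheses will be performed using one-sided tests with $\alpha = 0.10". The protocol (Study design) states "Couples will be randomized in a 1:1 ratio".

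Neither document gives the sample sizes behind the planning values or names the instrument behind the sleepiness means. The protocol lists the Epworth Sleepiness Scale among its questionnaires.

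**The concern.** The SAP labels the four values as SDs. If they describe people, about 95% of the We-PAP arm has a sleep efficiency between 79.9 and 84.5 and a sleepiness score between 4.3 and 5.5. The trial enrols patients with OSA and their bedpartners, and only one member of a couple needs elevated sleep disturbance, so better and poorer sleepers are mixed by design. So narrow a spread is hard to believe. Values of this size are what one sees when standard errors, or SDs of estimated means, are carried over as SDs.

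For these two outcomes the comparison with .54 has no other support. Sleep in both partners is part of the Aim 2 hypothesis, and Sample Size Determination mentions patient and partner sleep quality among the outcomes behind the sample size. A reader told that power is .8 for every outcome could take a null sleep result as evidence of no effect when the trial had little chance of detecting one.

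**Working it through.** **Inputs.** From the SAP: one-sided alpha .10; 20 couples per arm; within-couple r = .3; the means and SDs quoted above; CPAP hours 5.44 against 4 with SD 2.12. From the protocol: 1:1 randomisation of couples.

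**1. The plan's own figure.** Two people per couple give a design effect of 1 + .3 = 1.3, so the effective n per arm is 40/1.3 = 30.77. At d = .54 the noncentrality is .54 × √(30.77/2) = 2.118. Power is .799 by the normal approximation and .792 by noncentral t with 38 df. The detectable d at power .8 is .541 (normal). The figure reproduces, and the disputed SDs do not enter it.

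**2. Effects at face value.**
- Sleep efficiency: difference 82.2 − 79.99 = 2.21; pooled SD √((1.16² + 1.15²)/2) = 1.155; d = 2.21/1.155 = 1.91.
- Sleepiness: difference 5.2 − 4.9 = 0.3; pooled SD √((0.3² + 0.45²)/2) = 0.382; d = 0.3/0.382 = 0.78.

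Both exceed .54, so the comparison is correct on the numbers as printed.

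**3. Are they plausible as person-level SDs?**
- Distance from the arm mean covering about 95%: 1.96 × 1.16 = 2.27 efficiency points; 1.96 × 0.3 = 0.59 and 1.96 × 0.45 = 0.88 sleepiness points.
- SD as a share of the mean: 1.16/82.2 = 1.4%; 0.3/4.9 = 6%; 0.45/5.2 = 9%. For CPAP hours in the same section: 2.12/5.44 = 39% and 2.12/4 = 53%. The scales differ, so this is only a rough comparison.
- If sleepiness is a whole-number score (assumption), the smallest possible SD is √(f(1 − f)), where f is the fractional part of the mean: √(.9 × .1) = 0.30 at 4.9 and √(.2 × .8) = 0.40 at 5.2. The printed 0.3 equals its floor, which needs 90% of people scoring exactly 5 and 10% exactly 4. The printed 0.45 is just above its floor.
- d = 1.91 is far above the SAP's own .68 for CPAP hours and .7 for the other secondary outcomes.

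**4. Break-even SD for d = .54.** Sleep efficiency: 2.21/.54 = 4.09 points. Sleepiness: 0.3/.54 = 0.56 points.

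**5. If the values are standard errors** (assumption; source n per arm not given). Person-level SD = pooled value × √n. The break-even n is (4.093/1.155)² = 12.6 for efficiency and (0.5556/0.3824)² = 2.1 for sleepiness, so the comparison fails from n = 13 and n = 3. Power is by noncentral t, 38 df, pooled over both partners:

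| Source n per arm | Efficiency SD | d | Power | Sleepiness SD | d | Power |
|---|---|---|---|---|---|---|
| 10 | 3.65 | .61 | .86 | 1.21 | .25 | .37 |
| 20 | 5.17 | .43 | .65 | 1.71 | .18 | .27 |
| 40 | 7.30 | .30 | .46 | 2.42 | .12 | .21 |
| 80 | 10.33 | .21 | .33 | 3.42 | .09 | .17 |

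**6. What is untouched.** Outcomes with assumed d = .7 have power of about .92 (t) or .93 (normal). For CPAP hours, d = 1.44/2.12 = .68, and with 20 per arm power is .80 to .81.

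**The case against.** The strongest reply is that the arithmetic is right as printed: 1.91, 0.78 and .7 all exceed .54, and the documents nowhere say that the values are standard errors. That stands. This is a doubt about inputs, not a calculation error.

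Four stronger readings are tempting, and the documents support none of them.

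- *The values cannot be person-level SDs.* The whole-number floors do not show this: 0.3 sits at its floor and 0.45 above it, and sleep efficiency has no such bound. The floors also assume whole-number scoring, and the SAP does not name the sleepiness scale.
- *The stated power of .8 is wrong.* It reproduces without these SDs. Only its comparison with the assumed effects is affected, and only for two outcomes.
- *Both true assumed effects are below .54.* This depends on the person-level SDs. On the standard-error reading, sleep efficiency still passes with a source n of 12 (SD 4.00, d = .55, power .81). Sleepiness has far less room.
- *The actigraphy quality-control rule, "retraining will be assigned if scoring is not within 90% of the values determined by the co-PI", shows that an SD near 1 is impossible.* That rule triggers retraining of scorers. It says nothing about variation between people and has no bearing here.

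It is also fair to say that little in the trial turns on this. The go/no-go decision is tied to the primary adherence outcomes, CPAP hours are planned with their own SD, and the SAP already presents the study as a pilot that emphasises confidence intervals. That limits the weight of the point. It does not supply support for a statement made about all outcomes.

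**Conclusion.** The point holds as a defect in a planning claim. The printed SDs for sleep efficiency and daytime sleepiness are highly implausible as variation between people and look like standard errors or SDs of estimated means; only the cited sources can settle which. Until that is done, the coverage statement has no sound basis for these two outcomes.

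Its size depends on the true SDs. The margin is moderate for sleep efficiency and very thin for sleepiness, where a person-level SD of little more than half a point is enough to break the statement. Over assumed source arms of 10 to 80, power would run from .86 down to .33 for sleep efficiency and from .37 down to .17 for sleepiness. These ranges rest on the standard-error reading, the SAP's r = .3 and one-sided .10 level, and an effect pooled over patients and partners.

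**What to change.** In SAP section 4.4, Sample Size Determination:

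1. Check the four values against the cited sources, and state whether each is an SD or a standard error, with the source n per arm.
2. Name the scale behind the sleepiness means.
3. If they are standard errors, convert them to person-level SDs and recompute d and power for both outcomes.
4. Limit the coverage statement to outcomes whose recomputed d is at least .54. Describe any other as estimated with a confidence interval, without claiming .8 power. If the sources confirm person-level SDs, say so and keep the statement.

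The sample size, the analysis models and trial conduct stay as they are. The cost is a source check, an edit to the text, and possibly a less favourable stated power for up to two secondary outcomes.

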where i represents repeated measurement of the outcome variable, j represents individuals, and k represents couples. Treatment is a dummy coded variable with 0 = IC and 1 = We-PAP; Pre vs. 3 month follow-up is a dummy coded variable with 0 = pre-treatment and 1 = 3 month follow-up; and, patient vs. partner is a dummy coded variable with 0 = patient and 1 = partner. The level three intercept in this model, π_{0jk} , represents the maximum likelihood estimate of average outcome, π_{1jk} provides a test of differential treatment effects, and $\pi_{1[n+1]k}$ provides a test of whether these effects differ for patients and partners. Separate models will be run for each outcome.

Missing Data. Mechanisms of missingness will be evaluated in outcomes and potential mediators with missing data. If missingness patterns are consistent with MAR assumptions, recently developed fully conditional specification with chained equations methods for multiple imputation of missing data in MLMs will be used to handle missing data^{114,115}. All variables in hypothesis tests plus additional auxiliary variables will be included; potential auxiliary variables will be carefully screened using methods recommended for small sample sizes¹⁰³. If missingness patterns are consistent with MNAR assumptions, we will consider the use of pattern mixture models¹⁰⁴ and conditionally dependent dropout¹¹⁶ models to minimize any potential bias in estimation of treatment effects.

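### Maximum likelihood on 40 patients with no stated small-sample method makes the primary test slightly, and the 90% planning limit more noticeably, too favourable

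*SAP*

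**What the plan says.** The SAP's Analysis Plan for Aim 2 puts both primary outcomes into two-level models with daily CPAP records nested in patients: a Gaussian model for hours and a binomial model for nights of at least 4 hours. Treatment enters at the patient level. The intercept of the primary model "represents the maximum likelihood estimate of average adherence", and that of the three-level secondary models "represents the maximum likelihood estimate of average outcome".

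The General considerations in section 4.4 name the software ("All statistical analyses will be estimated using Stata v15 or higher") but no estimation option or reference distribution. They also say that "Any variables that emerge as being significantly different between the two treatment groups will be included as covariates"; when more than three variables differ, a single propensity score is used instead.

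Tests are one-sided at .10. Their role is stated: "We will use these criteria with the primary adherence outcomes as a go/no go threshold for proceeding to a larger scale RCT". For the next trial's size, "we will use the lower limit of the 90% CI to anticipate this reduction in effect size and conservatively plan for a larger study".

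The SAP's small-sample argument for these models is that groups of 20 give unbiased estimates. It does not extend this to standard errors, test level or coverage. Its other reference to small samples concerns the screening of auxiliary variables for imputation.

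**The concern.** However many nights are recorded, the treatment contrast is a comparison of 20 patients with 20. ML divides the between-patient sum of squares by 40 rather than by 40 minus the number of patient-level coefficients, so the standard error is too small. A normal rather than a t critical value would add to this. The effect grows with each patient-level covariate, and the plan adds covariates after looking at baseline imbalance.

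Two quantities that the SAP relies on would be affected: the .10 level of the go/no-go test, and the lower 90% limit, which is meant to be the cautious input for planning the next trial.

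**Working it through.** **Inputs.** From SAP section 4.4: 20 couples per group, one-sided alpha .10, 90% CI, means of 5.44 and 4 h, SD 2.12, d = .68, and up to three covariates or one propensity score. Assumptions: near-balanced nights and, where marked, a z reference.

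**1. The plan's own power figure.** The SAP says that "a sample size of 20 couples per group will provide power of .8 or higher". The assumed effect is 1.44/2.12 = .679. The noncentrality at d = .68 is .68 × √(20/2) = 2.150. The normal approximation gives Φ(2.150 − 1.282) = .808; the noncentral t with 38 df gives .801. The figure is reproduced, and it comes from a standard linear model, as the SAP says.

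**2. Test level and coverage, hours model.** In a balanced random-intercept model with k patient-level covariates, df = 40 − 2 − k, and the ML standard error equals the unbiased one times √(df/40). Hence

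- level = P(t_df > c₁ × √(df/40)), with c₁ = 1.2816 for z or the 90th percentile of t_df;
- coverage = P(|t_df| < c₂ × √(df/40)), with c₂ = 1.645 for z or the 95th percentile of t_df.

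| k | df | √(df/40) | ML with z: level | coverage | ML with t: level | coverage |
|---|---|---|---|---|---|---|
| 0 | 38 | .975 | .110 | .883 | .106 | .891 |
| 1 (or propensity score) | 37 | .962 | .113 | .878 | .109 | .887 |
| 3 | 35 | .935 | .119 | .867 | .115 | .877 |

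REML with z (factor 1) gives level .104 and coverage .892 (k = 0) or .891 (k = 3). REML with t gives .100 and .900. The documents give no dropout rate. If 30 patients were analysed, ML with z would give .113 to .127 and .877 to .854.

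**3. The decision threshold.** The standard error is 2.12 × √(2/20) = 0.670 h. With k = 0, a go needs a difference of 1.2816 × .975 × 0.670 = 0.84 h under ML with z, against 1.304 × 0.670 = 0.87 h under REML with t.

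**4. The planning limit.** Suppose 1.44 h with SD 2.12 is observed.

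- k = 0: ML with z, 1.44 − 1.645 × .975 × 0.670 = 0.365 h; REML with t, 1.44 − 1.686 × 0.670 = 0.310 h.
- k = 3, holding the unbiased standard error at 0.670: 0.409 h against 0.307 h.

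The SAP does not fix the next trial's design. If it is two-sided .05 with 80% power, n per arm = 2 × (1.960 + 0.842)² × (2.12/limit)². That is 529 against 736 per arm for k = 0, and 423 against 748 for k = 3.

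**5. Binomial model.** This was simulated with ML, 20 against 20 patients, 90 nights and an assumed random-intercept SD of 2 on the logit scale. With z, level and coverage were .109 and .884 (k = 0; 25,600 replicates) and .117 and .872 (k = 3; 17,600 replicates). A t reference alone left the level at .105 and .113.

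**6. Secondary models.** The differential treatment effect is treatment by time, and the equation for the time slope has no random term. With complete data it rests on 80 within-person changes and four coefficients, so df = 76. ML with z gives P(t₇₆ > 1.2816 × √(76/80)) = .108 and coverage .887. Baseline covariates enter only the intercept equation and cancel from the changes, so they do not raise this figure.

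**7. Unequal nights.** A fitted-model check with 30 to 90 nights per patient had only 318 replicates. Its level for ML with z was .121 for both k = 0 and k = 3, with Monte Carlo error of about .012. The direction agrees, but the check is too imprecise to replace the exact figures.

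**The case against.** The quoted sentence interprets an intercept. It states no reference distribution, and the reviewed text did not include all of the SAP, so the absence of a correction is inferred from silence. This stands for the z figures, which are conditional. It does not remove the point, because the ML variance bias remains under a t reference (.106 to .115).

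The three-covariate figure is an upper case. The documents give neither the number of baseline variables nor the level of their tests. If 10 to 20 independent variables are tested at .05, exactly three imbalances has probability .01 to .06 (at .10, .06 to .19). The usual excess is therefore about one point of alpha, on a threshold deliberately relaxed for a pilot. That stands.

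The sample-size contrast in step 4 is large mainly because the lower limit lies near zero, where any small change is magnified. That also stands; it is one scenario, not an expected error.

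A reader might draw three stronger conclusions that do not hold:

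- That switching to REML is enough. It leaves the level at .104 without a t reference, and it does not apply to the binomial model.
- That the secondary models share the primary inflation because they involve the same 40 couples. Step 6 shows a smaller figure that does not rise with baseline covariates.
- That the go/no-go rule is invalid. It moves by about 0.03 h.

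**Conclusion.** The point holds as a modest one. As described, the primary analysis is mildly liberal: by about one percentage point of test level without covariates and at most about two with three, with coverage one to three points short of 90%. These figures assume 40 analysed patients, near-balanced nights and a z reference; under a t reference they are roughly half as large without covariates and about three quarters as large with three. The go/no-go decision is barely affected. The lower 90% limit deserves more attention, because the SAP uses it as the conservative planning value and the error runs in the optimistic direction. The binomial result also depends on the assumed random-intercept SD.

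**What to change.** - **Gaussian models:** specify REML with Kenward-Roger (or Satterthwaite) degrees of freedom and t-based tests and intervals. If the planned multiple imputation is used, state small-sample degrees of freedom for the pooled results.
- **Binomial model for nights of at least 4 hours:** keep the prespecified model, and add a patient-level linear analysis of the percentage of such nights, with t-based inference, as a small-sample check. Say in advance how a disagreement between the two will be reported.
- **Next-trial sizing:** take the lower 90% limit for hours from the t-based interval.

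The cost is a few lines in the SAP, one short extra analysis, slightly larger p values and slightly wider intervals (the ML-with-z interval is 95% of the t-based width with no covariates and 91% with three). No patients are added: power at d = .68 is .801 with no covariates and .800 with three, which matches the linear-model basis of the SAP's own power calculation.
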